2.5.5 Pregnancies

The active pharmaceutical product in Xeris Pharmaceuticals' G-Pen™ is Glucagon, which is in Pregnancy Category B. Any subject found to be pregnant at any time during the study will be withdrawn from the study immediately. If a pregnancy is reported or initiated within 7 days following administration of the study medication, the pregnancy will be followed until resolution (i.e., birth or voluntary or spontaneous termination of the pregnancy) and reported using the pregnancy Case Report Form. Any pregnancy outcome that meets the criteria for an SAE will be reported both as a SAE and on the pregnancy Case Report Form.

A listing of pregnancies and outcomes will be presented (Listing 3).

3 STATISTICAL CONSIDERATIONS

3.1 Timing of Analyses

No interim analysis is planned for this study. The final analysis will be performed after the final database lock. There will be a single database lock after all data capture and cleaning is completed.

3.2 Analysis Cohort

The efficacy and PD analyses will include all participants who completed the dosing visit with the following exceptions:

- Dosing visits during which a glucose-elevating intervention is given after administration of G-Pen™ will be included in the analysis, but the glucose values after the additional intervention post-dosing will be censored.
- For the efficacy analysis, if the additional intervention is given before 30 minutes post-dosing, then the 30-minute post-dosing measurement will be replaced with the last glucose measurement prior to the intervention.
- For the PD analysis., if the additional intervention is given shortly after administration of G-Pen™ (i.e., more than half of the glucose values is censored), the subject will be excluded from the analysis.

3.3 Missing Data

For the efficacy analyses, last observation carried forward (LOCF) will be applied for subjects who drop out before 30 minutes post-dosing or who otherwise have missing primary endpoint data (e.g. missed blood draws). Baseline glucose is calculated as the mean of the initial glucose measurement <80 mg/dL and a second confirmatory measurement prior to dosing. If either one measurement is missing, then the available one will be used as the baseline glucose value. If both measurements are missing, the patient will not be included in the efficacy analyses, given there is no confirmation measurements the subject reached a blood glucose value of <80 mg/dL prior to receiving the glucagon injection. The proportion of non-analyzable subjects is expected to be low and will be monitored by the Clinical Research Associate (CRA) (or designee) throughout the trial.

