## 7.3. Interruption and Termination of Dosing

Dosing will be paused for any SAE which occurs in a subject receiving treatment until causality is fully assessed by the Investigator. Dosing will cease if the SAE is determined to be either drug-related or unknown, and may resume if the SAE is determined to be not drug-related by the investigator and the Sponsor is in agreement.

Visits in which glucagon is not given will not be included in the primary analyses. A visit will be considered completed for purposes of the sample size when glucagon is given and there is at least one blood glucose measurement 30 or more minutes after the glucagon injection.

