**Table 4: Schedule of Assessments**

Assessment	Screening	Treatment 1	Treatment 2*	Follow-up
	CRC Visit Day -30 to -3	CRC Visit Day 0	CRC Visit 7-28 days after first treatment	Phone call 3-14 days after each treatment
Informed consent	x	—	—	—
Inclusion/exclusion review	x	—	—	—
Height and weight	x	—	(x)	—
Physical exam a	x	—	—	—
Demographic data	x	—	—	—
Medical History	x	—	—	—
Concomitant medications	x	x b	x b	x b
Urine pregnancy test, if applicable	x	x	x	—
Hematology/Clinical chemistry	x	—	—	—
HbA1c	x	—	—	—
Vital signs	x	x	x	—
Overnight fast from midnight	—	x	x	—
Administration of study medication	—	x	x	—
Subject questionnaires for injection site discomfort	—	x	x	—
Draize scales for erythema/edema	—	x	x	—
Glucagon levels (PK) c	—	x	x	—
Venous blood glucose (PD) d	—	x	x	—
Adverse events (AE)	x	x	x	x b

\*Subjects ages 12-<18 only.

(x) Applies to weight only; repeat if >28 days have passed since the Treatment 1 visit.

a Excluding breast and pelvic/genital exams.

b Changes from prior visit.

c Venous blood at -5, 0, 10, 20, 30, 45, 60, 90, 120, and 180 minutes post dose, with ±2 minutes per collection for the samples from -5 and 0 minutes, and ±5 minutes for later samples.

d Via rapid glucose analyzer at -5, 0, and every 5 minutes post dose to 90 minutes, with ±2 minutes per collection.

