#### **13.2.1. Primary endpoint**

The primary endpoint is the change in plasma glucose at 30 minutes post-dosing from baseline, which is defined as the average of the two plasma glucose measurements (i.e., -5 and 0 minutes) completed immediately prior to dosing. Last observation carried forward (LOCF) will be applied for subjects who drop out before 30 minutes post-dosing or who otherwise have missing primary endpoint data (e.g. missed blood draws). In addition to the descriptive summary, a simple t-test will be used to compare the glucose change from baseline to zero change within each of the 3 age groups.

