2.4.2 Pharmacodynamic Endpoints

In the 12.0-<18.0 year-old age group, the plasma glucose change from baseline to 30 minutes after administration of G-Pen™ at a dose of 0.5 mg will be evaluated using the same approach described in Section 2.3.1 (Table 8).

Time for plasma glucose to increase by ≥ 25 mg/dL from baseline, maximum glucose concentration (C_{max}) between 0 and 90 min, the time to maximum concentration (T_{max}) will be directly obtained from the observed glucose concentration-time profile. If two identical values are recorded for C_{max} , the first one will be used for T_{max} . The area under the curve from 0 to 90 min (AUC_{0-90m}) of glucose will be calculated as the sum of areas of trapezoids, which are composed of adjacent glucose values. The following rules will be considered:

1. If there are missing data points before the last observed value, they will not be imputed.
2. If there are missing data points after the last observed value, they will be extrapolated using the last two data points.

Baseline-adjusted AUC_{0-90m} with negative values set at 0 will also be calculated. All PD endpoints will be analyzed descriptively for each age group (Table 9) and by treatment dose for subjects aged 12.0-<18.0 (Table 10). Actual time instead of protocol time will be used for calculating the time for plasma glucose to increase by ≥ 25 mg/dL from baseline, T_{max} , AUC_{0-90m} , and baseline-adjusted AUC_{0-90m} . In addition, plasma glucose concentration-time profile by age group (Figure 2 and Table 11) and by treatment dose for subjects aged 12.0-<18.0 (Figure 3 and Table 11) will be presented.

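### LOCF is applied to an isolated missed 30-minute glucose draw even when a reading just after 30 minutes is on file, which biases that child's change in a direction set by the curve

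*SAP*

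**What the plan says.** The primary endpoint is the change in plasma glucose from baseline (mean of the -5 and 0 minute readings) to 30 minutes after dosing, analysed within each age group (protocol 13.2.1, SAP 2.3.1).

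For a missing 30-minute value, SAP 3.3 has two triggers. The first is dropout: "last observation carried forward (LOCF) will be applied for subjects who drop out before 30 minutes post-dosing". The second is any other cause: "or who otherwise have missing primary endpoint data (e.g. missed blood draws". Protocol 13.2.1 carries the same rule, beginning "Last observation carried forward (LOCF) will be applied for subjects who drop out before 30 minutes post-dosing". Neither section asks whether a later reading exists.

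Other parts of the plan bear on this:

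- Protocol Table 4 schedules bedside glucose "every 5 minutes post dose to 90 minutes, with ±2 minutes per collection". A single missed 30-minute draw would normally have neighbours at about 25 and 35 minutes.
- SAP 2.4.2 says of the glucose AUC that it "will be calculated as the sum of areas of trapezoids, which are composed of adjacent glucose values", and of interior gaps: "If there are missing data points before the last observed value, they will not be imputed". Together these join the readings on either side of a gap with a straight line, at actual times.
- Protocol 7.3 counts a visit towards the sample size when glucagon was given and "there is at least one blood glucose measurement 30 or more minutes after the glucagon injection".
- SAP 3.2 has a separate rule when a glucose-elevating intervention is given before 30 minutes: "then the 30-minute post-dosing measurement will be replaced with the last glucose measurement prior to the intervention". Values after the intervention are censored.

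**The concern.** A child who drops out before 30 minutes has no later reading, so the plan must fall back on something like LOCF. A child who misses one draw and continues is different. The 25- and 35-minute readings bracket the missing value, and the written rule discards the later one. Holding the 25-minute value flat for 5 minutes is right only if glucose is not changing then.

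Each age group is planned with 6 evaluable children, so one child is a sixth of the cohort mean. SAP 1.2.1 says the endpoint is meant to quantify the increase, not only to test it against zero, so an avoidable error in either direction matters for the estimate.

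**Working it through.** **Inputs**

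| Input | Value | Source |
|---|---|---|
| Mean rise at 30 min, SD | 25 mg/dL, 18 | SAP 1.3 |
| Mean rise at 30 min, SD | 35 mg/dL, 18 | Protocol 13.1 |
| Evaluable children per age group | 6 | SAP 1.3, protocol 9.1 |
| Test | t-test against zero, two-sided 0.05 | SAP 2.3.1 |
| Glucose readings | every 5 min to 90 min, ±2 min | Protocol Table 4 |
| Curve shape or peak time | not given | assumed below |

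**1. The plan's own figure.** Normal approximation with 25 and 18: n = ((1.960 + 1.282) × 18 / 25)² = 2.334² = 5.45, rounded up to 6. The planned size reproduces. With the two-sided t-test on 5 degrees of freedom, power at n = 6 is 77.5% for a rise of 25 and 96.3% for a rise of 35. The two documents give different rises for the same earlier study. That is a separate matter; both values are used here as a range.

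**2. LOCF from 25 minutes, assuming a straight-line rise R over 30 minutes.** Carried change = R × 25/30; error = −R × 5/30.

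- R = 25: carried 20.8, error −4.2 mg/dL.
- R = 35: carried 29.2, error −5.8 mg/dL.

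**3. Interpolation on the same line.** Value = G(a) + (30 − a)/(b − a) × (G(b) − G(a)), with a = 25 and b = 35.

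- R = 25: (20.83 + 29.17)/2 = 25.0.
- R = 35: (29.17 + 40.83)/2 = 35.0.

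The error is zero by construction, so other shapes are tried in step 5.

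**4. Effect on a group of 6 with one affected child.** 4.17/6 = 0.7 and 5.83/6 = 1.0 mg/dL. The standard error of the mean is 18/√6 = 7.3 mg/dL. Holding the SD at 18, power goes from 77.5% to 75.3% (rise of 25) or from 96.3% to 95.4% (rise of 35).

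**5. Other assumed curves, scaled to a 30-minute change of 25 or 35.** One-peak form: (t/p)·exp(1 − t/p), with the peak at p minutes. Sigmoid form: t^h/(t^h + m^h), with m = 15, 20 or 30 and h = 2 or 4; its figures for 35 are those for 25 times 35/25 = 1.4.

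| Curve | LOCF error, 25 / 35 (mg/dL) | Interpolation error, 25 / 35 (mg/dL) |
|---|---|---|
| Peak at 15 min | +4.1 / +5.7 | 0.0 / 0.0 |
| Peak at 20 min | +1.8 / +2.5 | −0.3 / −0.4 |
| Peak at 25 min | +0.5 / +0.6 | −0.3 / −0.5 |
| Peak at 30 min | −0.4 / −0.5 | −0.4 / −0.5 |
| Peak at 45 min | −1.7 / −2.4 | −0.3 / −0.4 |
| Peak at 90 min | −3.0 / −4.2 | −0.2 / −0.3 |
| Sigmoid, smallest error | −1.5 / −2.1 | −0.3 / −0.4 |
| Sigmoid, largest error | −8.7 / −12.2 | −0.9 / −1.2 |

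The sign of the LOCF error follows the slope just before 30 minutes. Interpolation stays within about 1 mg/dL throughout. If the peak falls at about 27 to 30 minutes the two methods differ by less than 0.5 mg/dL, and LOCF can be marginally the closer.

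**The case against.** The strongest defence is that LOCF is prespecified, that protocol and SAP agree on it, and that the effect is small. One affected child moves a mean of 6 by about 1 mg/dL, against a standard error of about 7.3. If glucose is still rising, the error works against the drug in a single-arm test against zero and cannot favour a false positive. The size argument stands. The conservatism argument holds only if glucose is rising, and it does not answer the aim of quantifying the rise.

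A reader might infer four stronger things. The documents do not support them.

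- **That LOCF always understates the rise.** No section gives a peak time or curve shape, and glucose Tmax is itself an outcome. The synopsis expects at least 25 mg/dL by 30 minutes, which does not say that glucose is still climbing then. An early peak makes LOCF overstate.
- **That the blood-volume cap makes missed 30-minute draws likely.** The same rule (protocol 11.1) prefers collections from -5 to 30 minutes over later ones and puts glucose ahead of glucagon samples. It protects this reading.
- **That a child counted as complete under protocol 7.3 could be scored as having almost no rise.** This needs all six readings from 5 to 30 minutes lost and a pre-dose value carried forward as the response, which neither section states. Protocol 7.3 defines completion for the sample size, not the 30-minute value.
- **That the AUC rule contradicts the LOCF rule.** An area can be summed across a gap without imputing anything, while a single-timepoint endpoint needs a value. The contrast shows that the neighbouring readings are usable, not that the plan is inconsistent.

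**Conclusion.** The point holds in limited form. As written, both documents require LOCF for an isolated missed 30-minute draw even when a bracketing later reading is available. The resulting error for that child is downward if glucose is still rising and upward if it has already peaked. Under the straight-line assumption it is about 4.2 to 5.8 mg/dL low for the child and 0.7 to 1.0 mg/dL on a mean of 6.

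These figures rest on an assumed curve, on one affected child in 6, and on a last reading at 25 minutes. The documents give no expected rate of missed draws, and such cases should be few. The case for change is that a better value would normally be on file at almost no cost, not that the primary result is at risk. Label: cheap improvement.

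**What to change.** In SAP 3.3 and protocol 13.2.1, add a rule such as:

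> When the 30-minute glucose value is missing, and the adjacent scheduled readings before and after it (about 25 and 35 minutes) are available within the prespecified maximum gap and neither is censored because of a glucose-elevating intervention, the value is obtained by linear interpolation between them at actual times. LOCF applies when no usable later reading exists within that gap.

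The maximum gap must be stated, because interpolating between any two readings on either side would allow a line drawn across an unseen peak. With ±2-minute windows the neighbours can lie at most 37 − 23 = 14 minutes apart, so a limit of 14 minutes would admit every in-window pair and nothing much wider.

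Leave the intervention rule of SAP 3.2 as it is. Values after an intervention must not enter the interpolation.

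The cost is one extra prespecified rule, a few lines of code and no new data. It should be settled before database lock.

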3.4 Interim Analyses and Data Monitoring

As detailed in Section 15.3 of the protocol, the CRA (or designee) will review and evaluate each related AE in addition to accumulated trial data for participant safety, trial conduct and trial progress after trial initiation. Since this is a single-arm trial, safety results will be listed in an unblinded fashion and reviewed by the Sponsor regularly. There will be no interim analysis of the efficacy endpoint planned for this study.

3.5 Multicenter Studies

Data will be pooled within each age group across all clinical sites. Center effects are not anticipated because the sites are using standardized procedures for treatment with G-Pen™ and assessment of solicited and unsolicited adverse events.

3.6 Multiple Comparisons/Multiplicity

There is only one primary endpoint. Each age group is individually powered. No adjustments for multiple testing are planned.

3.7 Covariates and Subgroups

Neither covariate adjustments nor additional subgroup analyses are planned for this study.

4 REPORTING CONVENTIONS

P-values ≥ 0.001 and ≤ 0.999 will be reported to 3 decimal places; *P*-values less than 0.001 will be reported as “<0.001”; *P*-values greater than 0.999 will be reported as “>0.999”. The mean, standard deviation (SD), and any other statistics other than quantiles, will be reported to one decimal place greater than the original data. Quantiles, such as median, or minimum and maximum will use the same number of decimal places as the original data.

5 TECHNICAL DETAILS

SAS version 9.4 will be used to generate all tables, figures and listings and perform statistical analyses, and Phoenix WinNonLin version 6.4 will be used to perform the PD analysis.

APPENDICES

Appendix I: TABLE/FIGURE/LISTING MOCK-UPS

Appendix II: PHARMACOKINETIC ANALYSIS (CONDUCTED BY INTEGRATED MEDICAL DEVELOPMENT, NEW JERSEY USA)

Appendix I: TABLE/FIGURE/LISTING MOCK-UPS

Demographic Data

Figure 1: Study flow chart

[figure not shown]

Table 1: Ineligibility summary of screen failures

Inclusion/Exclusion Category	Inclusion/Exclusion Criterion	Number of Subjects who did not meet the criteria ^a
Inclusion and Exclusion	Number of subjects failing any eligibility criterion	x
Inclusion	Any inclusion criterion	x
	1. Subject is a male or female diagnosed with T1D for at least 6 months at Screening	x
	2. Subject is currently using daily insulin treatment	x
	3. Subject is at least 2.0 and less than 18.0 years of age, and will be <18.0 for the duration of the study	x
	4. Subject and adult guardian are willing to follow all study procedures, including attending all clinic visits	x
	5. Parent or guardian has provided written informed consent, and assent has been obtained from subjects if appropriate for age according to IRB requirements	x
Exclusion	Any exclusion criterion	x
	1. Subject is pregnant and/or nursing	x
	2. Subject has renal insufficiency (serum creatinine >1.5 mg/dL in males or >1.4 mg/dL in females)	x
	3. Subject has serum ALT > 3 times the upper limit of normal	x
	4. Subject has serum AST > 3 times the upper limit of normal	x
	5. Subject has hepatic synthetic insufficiency as defined as a serum albumin of <3.0 g/dL	x
	6. Subject has serum bilirubin >2.0 mg/dL	x
	7. Subject has hematocrit of <30%	x
	8. Subject has mean of triplicate blood pressure readings at Screening where systolic blood pressure or diastolic blood pressure was >95% of normal for age and height percentile	x
	9. Subject uses >2.0 U/kg total insulin dose per day	x

Table 1: Ineligibility summary of screen failures

Inclusion/Exclusion Category	Inclusion/Exclusion Criterion	Number of Subjects who did not meet the criteria ^a
	10. Subject has inadequate venous access	x
	11. Subject has a current seizure disorder	x
	12. Subject has a history of pheochromocytoma or a disorder with increased risk of pheochromocytoma (e.g. MEN 2, neurofibromatosis, or Von Hippel-Lindau disease)	x
	13. Subject has a history of insulinoma	x
	14. Subject has a history of allergies to glucagon or glucagon-like products, or any history of significant hypersensitivity to glucagon or any related products or to any of the excipients (DMSO and trehalose) in the investigational formulation	x
	15. Subject has a history of glycogen storage disease	x
	16. Subject has any concurrent illness, other than diabetes, that is not controlled by a stable therapeutic regimen	x
	17. Subject is an active user of alcohol or drugs of abuse	x
	18. Subject has had an administration of glucagon within 14 days of the first treatment visit	x
	19. Subject has participated in other studies involving administration of an investigational drug or device within 30 days or 5 half-lives, whichever is longer, before Screening for the current study and during participation in the current study	x
	20. The principal investigator deems this subject exclusionary	x

^a A subject may fail to meet more than one eligibility criteria.

Table 2: Subject disposition by age group

Subject Disposition	Age Group					
	2.0-<6.0 years (N=X)		6.0-<12.0 years (N=X)		12.0-<18.0 years (N=X)	
	n	%	n	%	n	%
Screened	x	x.x	x	x.x	x	x.x
Enrolled	x	x.x	x	x.x	x	x.x
Received All Scheduled Treatments^a	x	x.x	x	x.x	x	x.x
Completed All Study Follow-ups^b	x	x.x	x	x.x	x	x.x

^a Refer to Table 3 for reasons subjects discontinued treatment or terminated early.

^b Refer to Table 4 for reasons subjects who did not complete the follow-up phone call.

Table 3: Reasons for discontinued treatment or early termination by age group

Category	Reason	Age Group					
		2.0-<6.0 years (N=X)		6.0-<12.0 years (N=X)		12.0-<18.0 years (N=X)	
		n	%	n	%	n	%
Early Termination Prior to Treatment 1 Visit	Subject did not fast for at least 8 hours	x	x.x	x	x.x	x	x.x
	Subject has severe hypoglycemic event within last 2 weeks	x	x.x	x	x.x	x	x.x
	Ketone results were moderate or greater	x	x.x	x	x.x	x	x.x
	Subject decision	x	x.x	x	x.x	x	x.x
	Investigator/Physician decision	x	x.x	x	x.x	x	x.x
	Sponsor decision	x	x.x	x	x.x	x	x.x
	Other reason	x	x.x	x	x.x	x	x.x
Discontinued After Treatment 1 Visit	Withdrawal early due to adverse event	x	x.x	x	x.x	x	x.x
	Missed visits, lost to follow-up, or lack of cooperation	x	x.x	x	x.x	x	x.x
	Voluntary withdrawal	x	x.x	x	x.x	x	x.x
	Terminated early due to protocol deviation	x	x.x	x	x.x	x	x.x
	Death	x	x.x	x	x.x	x	x.x
Early Termination Prior to	Subject did not fast for at least 8 hours	NA		NA		x	x.x

Table 3: Reasons for discontinued treatment or early termination by age group

Category	Reason	Age Group					
		2.0-<6.0 years (N=X)		6.0-<12.0 years (N=X)			
		n	%	n	%		
Treatment 2 Visit (12.0 - <18.0 year-old only)	Subject has severe hypoglycemic event within last 2 weeks	NA		NA		x	x.x
	Ketone results were moderate or greater	NA		NA		x	x.x
	Subject decision	NA		NA		x	x.x
	Investigator/Physician decision	NA		NA		x	x.x
	Sponsor decision	NA		NA		x	x.x
	Other reason	NA		NA		x	x.x

NA=not applicable.

Table 4: Completion rate of follow-up phone call after each treatment visit by age group

Follow-up Phone Call Assessment	Age Group					
	2.0-<6.0 years (N=X)		6.0-<12.0 years (N=X)		12.0-<18.0 years (N=X)	
	n	%	n	%	n	%
Completed After Treatment Visit 1						
Yes	X	X.X	X	X.X	X	X.X
No	X	X.X	X	X.X	X	X.X
Reason 1	X	X.X	X	X.X	X	X.X
Reason 2	X	X.X	X	X.X	X	X.X
Completed After Treatment Visit 2						
Yes	NA		NA		X	X.X
No	NA		NA		X	X.X
Reason 1	NA		NA		X	X.X
Reason 2	NA		NA		X	X.X

NA=not applicable.

Table 5: Distribution of protocol deviations
A. Subject-specific protocol deviations by age group

Category	Age Group					
	2.0-<6.0 years (N=X)		6.0-<12.0 years (N=X)		12.0-<18.0 years (N=X)	
	No. of Subjects	No. of Deviations	No. of Subjects	No. of Deviations	No. of Subjects	No. of Deviations
Any Category	XX	XX	XX	XX	XX	XX
Informed consent procedures	XX	XX	XX	XX	XX	XX
Eligibility/exclusion criteria	XX	XX	XX	XX	XX	XX
Missed scheduled study	XX	XX	XX	XX	XX	XX
Scheduled visit/procedure conducted outside of window	XX	XX	XX	XX	XX	XX
Laboratory assessment not performed	XX	XX	XX	XX	XX	XX
Study procedure/ assessment not performed	XX	XX	XX	XX	XX	XX
Procedure/assessment not performed per protocol	XX	XX	XX	XX	XX	XX
Temperature excursion	XX	XX	XX	XX	XX	XX
Specimen excursion	XX	XX	XX	XX	XX	XX
Specimen collected outside of window	XX	XX	XX	XX	XX	XX
Other	XX	XX	XX	XX	XX	XX

Table 5: Distribution of protocol deviations (continued)**B. Study-specific protocol deviation by site**

Category	No. of Deviations at Each Site							
	Barbara Davis Center for Childhood Diabetes	Women & Children's Hospital of Buffalo	University of Florida Diabetes Institute	Riley Hospital for Children at IU Health	University of Iowa Hospitals and Clinics	Nemours Children's Clinic	Lucile Packard Children's Hospital at Stanford	Yale University School of Medicine
Any Category	XX	XX	XX	XX	XX	XX	XX	XX
Informed consent procedures	XX	XX	XX	XX	XX	XX	XX	XX
Eligibility/exclusion criteria	XX	XX	XX	XX	XX	XX	XX	XX
Missed scheduled study	XX	XX	XX	XX	XX	XX	XX	XX
Scheduled visit/procedure conducted outside of window	XX	XX	XX	XX	XX	XX	XX	XX
Laboratory assessment not performed	XX	XX	XX	XX	XX	XX	XX	XX
Study procedure/ assessment not performed	XX	XX	XX	XX	XX	XX	XX	XX
Procedure/assessment not performed per protocol	XX	XX	XX	XX	XX	XX	XX	XX
Temperature excursion	XX	XX	XX	XX	XX	XX	XX	XX
Specimen excursion	XX	XX	XX	XX	XX	XX	XX	XX
Specimen collected outside of window	XX	XX	XX	XX	XX	XX	XX	XX
Other	XX	XX	XX	XX	XX	XX	XX	XX

Listing 1: Listing of protocol deviations by site

Site	Date Deviation identified	Subject-specific Deviation?	Subject ID	Treatment Group	Deviation Category	Deviation Description	Resulted in Subject Termination?	Deviation Severity	Deviation Resolution

Table 6: Demographic and baseline clinical characteristics by age group

	Age Group		
	2.0-<6.0 years (N=X)	6.0-<12.0 years (N=X)	12.0-<18.0 years (N=X)
Age, years			
N	x	x	x
Mean (SD)	xx.xx (xx.xx)	xx.xx (xx.xx)	xx.xx (xx.xx)
Median	xx.x	xx.x	xx.x
[Min-Max]	[xx.x-xx.x]	[xx.x-xx.x]	[xx.x-xx.x]
Gender – n (%)			
Male	x (x.x)	x (x.x)	x (x.x)
Female	x (x.x)	x (x.x)	x (x.x)
Ethnicity – n (%)			
Hispanic or Latino	x (x.x)	x (x.x)	x (x.x)
Not Hispanic or Latino	x (x.x)	x (x.x)	x (x.x)
Race – n (%)			
White	x (x.x)	x (x.x)	x (x.x)
Black/African American	x (x.x)	x (x.x)	x (x.x)
Native Hawaiian/Other Pacific Islander	x (x.x)	x (x.x)	x (x.x)
Asian	x (x.x)	x (x.x)	x (x.x)
American Indian/Alaskan Native	x (x.x)	x (x.x)	x (x.x)
Multi-Racial	x (x.x)	x (x.x)	x (x.x)

Table 6: Demographic and baseline clinical characteristics by age group

	Age Group		
	2.0-<6.0 years (N=X)	6.0-<12.0 years (N=X)	12.0-<18.0 years (N=X)
Body Mass Index^a, kg/m²			
N	x	x	x
Mean (SD)	xx.xx (xx.xx)	xx.xx (xx.xx)	xx.xx (xx.xx)
Median	xx.x	xx.x	xx.x
[Min-Max]	[xx.x-xx.x]	[xx.x-xx.x]	[xx.x-xx.x]
Duration of Type 1 Diabetes, years			
N	x	x	x
Mean (SD)	xx.xxx (xx.xxx)	xx.xxx (xx.xxx)	xx.xx (xx.xxx)
Median	xx.xx	xx.xx	xx.xx
[Min-Max]	[xx.xx-xx.xx]	[xx.xx-xx.xx]	[xx.xx-xx.xx]
Hemoglobin A1c, %			
N	x	x	x
Mean (SD)	xx.xx (xx.xx)	xx.xx (xx.xx)	xx.xx (xx.xx)
Median	xx.x	xx.x	xx.x
[Min-Max]	[xx.x-xx.x]	[xx.x-xx.x]	[xx.x-xx.x]
Primary Insulin Modality – n (%)			
Insulin pump	x (x.x)	x (x.x)	x (x.x)
Insulin injections	x (x.x)	x (x.x)	x (x.x)
Both pump and injections	x (x.x)	x (x.x)	x (x.x)

Table 6: Demographic and baseline clinical characteristics by age group

	Age Group		
	2.0-<6.0 years (N=X)	6.0-<12.0 years (N=X)	12.0-<18.0 years (N=X)
Average Daily Insulin Dose for Pumpers, total units			
N	x	x	x
Mean (SD)	xxx.x (xxx.x)	xxx.x (xxx.x)	xxx.x (xxx.x)
Median	xxx	xxx	xxx
[Min-Max]	[xxx-xxx]	[xxx-xxx]	[xxx-xxx]
Number of Injections Per Day for Injectors			
N	x	x	x
Mean (SD)	xx.x (xx.x)	xx.x (xx.x)	xx.x (xx.x)
Median	xx	xx	xx
[Min-Max]	[xx-xx]	[xx-xx]	[xx-xx]
Clinical Site – n (%)			
Barbara Davis Center for Childhood Diabetes	x (x.x)	x (x.x)	x (x.x)
Women & Children's Hospital of Buffalo	x (x.x)	x (x.x)	x (x.x)
University of Florida Diabetes Institute	x (x.x)	x (x.x)	x (x.x)
Riley Hospital for Children at IU Health	x (x.x)	x (x.x)	x (x.x)
University of Iowa Hospitals and Clinics	x (x.x)	x (x.x)	x (x.x)
Nemours Children's Clinic	x (x.x)	x (x.x)	x (x.x)
Lucile Packard Children's Hospital at Stanford	x (x.x)	x (x.x)	x (x.x)
Yale University School of Medicine	x (x.x)	x (x.x)	x (x.x)

^a Calculated as weight in kilograms divided by height in meters squared.
 SD=standard deviation.

Efficacy Data

Table 7: Plasma glucose before and 30 minutes after administration of G-Pen™ by age group				
Age Group	Plasma Glucose (mg/dL) Mean (SD), median, [min – max]			P-value^a
	Baseline	30 minutes	Change	
2.0-<6.0 years (N=X)	xx.x (xx.x), xx, [xx-xx]	xxx.x (xxx.x), xxx, [xxx-xxx]	xxx.x (xxx.x), xxx, [xxx-xxx]	x.XXX
6.0-<12.0 years (N=X)	xx.x (xx.x), xx, [xx-xx]	xxx.x (xxx.x), xxx, [xxx-xxx]	xxx.x (xxx.x), xxx, [xxx-xxx]	x.XXX
12.0-<18.0 years (N=X)	xx.x (xx.x), xx, [xx-xx]	xxx.x (xxx.x), xxx, [xxx-xxx]	xxx.x (xxx.x), xxx, [xxx-xxx]	x.XXX

^a P-value computed using *t*-test for testing whether the change in glucose from baseline to 30 minutes is zero.

SD= standard deviation.

Table 8: Plasma glucose before and 30 minutes after administration of G-Pen™ in the 12.0-<18.0 year-old age group at a dose of 0.5 mg

Age Group	Plasma Glucose (mg/dL) Mean (SD), median, [min – max]			P-value^a
	Baseline	30 minutes	Change	
12.0-<18.0 years (N=X)	xx.x (xx.x), xx, [xx-xx]	xxx.x (xxx.x), xxx, [xxx-xxx]	xxx.x (xxx.x), xxx, [xxx-xxx]	x.xxx

^a P-value computed using t-test for testing whether the change in glucose from baseline to 30 minutes is zero.

SD= standard deviation.

Table 9: Plasma glucose AUC_{0-90m}, C_{max}, T_{max}, and time to increase by ≥25 mg/dL from baseline by age group

Age Group	G-Pen™ Dose	Summary Statistics	C _{max} (mg/dL)	T _{max} (min)	AUC _{0-90m} (min*mg/dL)	Baseline-adjusted AUC _{0-90m} (min*mg/dL)	Time to increase by ≥25 mg/dL from baseline
2.0-<6.0 years	0.5 mg	N	x	x	x	x	x
		Mean (SD)	xxx.x (xxx.x)	xx.x (xx.x)	xxx.x (xxx.x)	xxx.x (xxx.x)	xx.x (xx.x)
		Median	xxx	xx	xxx	xxx	xx
		[Min-Max]	[xxx-xxx]	[xx-xx]	[xxx-xxx]	[xxx-xxx]	[xx-xx]
6.0-<12.0 years	0.5 mg	N	x	x	x	x	x
		Mean (SD)	xxx.x (xxx.x)	xx.x (xx.x)	xxx.x (xxx.x)	xxx.x (xxx.x)	xx.x (xx.x)
		Median	xxx	xx	xxx	xxx	xx
		[Min-Max]	[xxx-xxx]	[xx-xx]	[xxx-xxx]	[xxx-xxx]	[xx-xx]
12.0-<18.0 years	1.0 mg	N	x	x	x	x	x
		Mean (SD)	xxx.x (xxx.x)	xx.x (xx.x)	xxx.x (xxx.x)	xxx.x (xxx.x)	xx.x (xx.x)
		Median	xxx	xx	xxx	xxx	xx
		[Min-Max]	[xxx-xxx]	[xx-xx]	[xxx-xxx]	[xxx-xxx]	[xx-xx]

AUC= area under the curve; C_{max}= maximum plasma concentration; T_{max}= time to maximum plasma concentration; SD= standard deviation.

Table 10: Plasma glucose AUC_{0-90m}, C_{max}, T_{max}, and time to increase by ≥ 25 mg/dL from baseline by treatment dose for subjects aged 12.0-<18.0

G-Pen™ Dose	Summary Statistics	C _{max} (mg/dL)	T _{max} (min)	AUC _{0-90m} (min*mg/dL)	Baseline-adjusted AUC _{0-90m} (min*mg/dL)	Time to increase by ≥ 25 mg/dL from baseline
1.0 mg	N	x	x	x	x	x
	Mean (SD)	xxx.x (xxx.x)	xx.x (xx.x)	xxx.x (xxx.x)	xxx.x (xxx.x)	xx.x (xx.x)
	Median	xxx	xx	xxx	xxx	xx
	[Min-Max]	[xxx-xxx]	[xx-xx]	[xxx-xxx]	[xxx-xxx]	[xx-xx]
0.5 mg	N	x	x	x	x	x
	Mean (SD)	xxx.x (xxx.x)	xx.x (xx.x)	xxx.x (xxx.x)	xxx.x (xxx.x)	xx.x (xx.x)
	Median	xxx	xx	xxx	xxx	xx
	[Min-Max]	[xxx-xxx]	[xx-xx]	[xxx-xxx]	[xxx-xxx]	[xx-xx]

AUC= area under the curve; C_{max}= maximum plasma concentration; T_{max}= time to maximum plasma concentration; SD= standard deviation.

[figure not shown]
Figure 2: Plasma glucose over time by age group

[figure not shown]
Figure 3: Plasma glucose over time by treatment dose for subjects aged 12.0-<18.0

Table 11: Plasma glucose over time by age group and by treatment dose for subjects aged 12.0-<18.0

Plasma Glucose, mg/dL Mean (SD)		Time (min)																			
Age Group	G-Pen™ Dose	-5	0	5	10	15	20	25	30	35	40	45	50	55	60	65	70	75	80	85	90
2.0-<6.0 years (N=X)	0.5 mg	xx.x (xx.x)	xx.x (xx.x)	xxx.x (xxx.x)																	
6.0-<12.0 years (N=X)	0.5 mg	xx.x (xx.x)	xx.x (xx.x)	xxx.x (xxx.x)																	
12.0-<18.0 years (N=X)	1.0 mg	xx.x (xx.x)	xx.x (xx.x)	xxx.x (xxx.x)																	
12.0-<18.0 years (N=X)	0.5 mg	xx.x (xx.x)	xx.x (xx.x)	xxx.x (xxx.x)																	

SD= standard deviation.

Safety Data

Table 12: Number and percentage of subjects experiencing adverse events by MedDRA® system organ class and preferred term, and treatment dose						
Non-treatment emergent adverse events (non-TEAE)						
MedDRA® System Organ Class (SOC)	MedDRA® Preferred Term (PT)	G-Pen™ Dose				
		0.5 mg (N=X)		1.0 mg (N=X)		
		n	%	n	%	
Any SOC	Any PT	xx	x.x	x	x.x	
[SOC 1]	Any PT	xx	x.x	x	x.x	
	[PT 1]	xx	x.x	x	x.x	
	[PT 2]	xx	x.x	x	x.x	
[SOC 2]	Any PT	xx	x.x	x	x.x	
	[PT 1]	xx	x.x	x	x.x	
	[PT 2]	xx	x.x	x	x.x	

¹Note: This table presents number and percentage of subjects. A subject is only counted once per PT. A subject may have multiple PTs.

²Any SAE occurred will be summarized in the footnote.

Table 12: Number and percentage of subjects experiencing adverse events by MedDRA® system organ class and preferred term, and treatment dose (continued)

Treatment emergent adverse events (TEAE)						
MedDRA® System Organ Class (SOC)	MedDRA® Preferred Term (PT)	G-Pen™ Dose				
		0.5 mg (N=X)		1.0 mg (N=X)		
		n	%	n	%	
Any SOC	Any PT	xx	x.X	x	x.X	
[SOC 1]	Any PT	xx	x.X	x	x.X	
	[PT 1]	xx	x.X	x	x.X	
	[PT 2]	xx	x.X	x	x.X	
[SOC 2]	Any PT	xx	x.X	x	x.X	
	[PT 1]	xx	x.X	x	x.X	
	[PT 2]	xx	x.X	x	x.X	

¹Note: This table presents number and percentage of subjects. A subject is only counted once per PT. A subject may have multiple PTs.

²Any SAE occurred will be summarized in the footnote.

Table 13: Severity of adverse events and their relatedness to study by MedDRA® system organ class and preferred term, and treatment dose**Non-treatment emergent adverse events (non-TEAE)**

MedDRA® System Organ Class (SOC)	MedDRA® Preferred Term (PT)	G-Pen™ Dose																			
		0.5 mg (N=X)										1.0 mg (N=X)									
		Severity				Relatedness				Severity				Relatedness				Study Drug		Study Device	
		Mild		Moderate		Severe		Study Drug		Study Device		Study Procedure		Mild		Moderate		Severe		Study Drug	
		n	%	n	%	n	%	n	%	n	%	n	%	n	%	n	%	n	%	n	%
Any SOC	Any PT	xx	xx.x	xx	xx.x	xx	xx.x	xx	xx.x	xx	xx.x	xx	xx.x	xx	xx.x	xx	xx.x	xx	xx.x	xx	xx.x
[SOC 1]	Any PT	xx	xx.x	xx	xx.x	xx	xx.x	xx	xx.x	xx	xx.x	xx	xx.x	xx	xx.x	xx	xx.x	xx	xx.x	xx	xx.x
	[PT 1]	xx	xx.x	xx	xx.x	xx	xx.x	xx	xx.x	xx	xx.x	xx	xx.x	xx	xx.x	xx	xx.x	xx	xx.x	xx	xx.x
	[PT 2]	xx	xx.x	xx	xx.x	xx	xx.x	xx	xx.x	xx	xx.x	xx	xx.x	xx	xx.x	xx	xx.x	xx	xx.x	xx	xx.x
[SOC 2]	Any PT	xx	xx.x	xx	xx.x	xx	xx.x	xx	xx.x	xx	xx.x	xx	xx.x	xx	xx.x	xx	xx.x	xx	xx.x	xx	xx.x
	[PT 1]	xx	xx.x	xx	xx.x	xx	xx.x	xx	xx.x	xx	xx.x	xx	xx.x	xx	xx.x	xx	xx.x	xx	xx.x	xx	xx.x
	[PT 2]	xx	xx.x	xx	xx.x	xx	xx.x	xx	xx.x	xx	xx.x	xx	xx.x	xx	xx.x	xx	xx.x	xx	xx.x	xx	xx.x

¹Note: This table presents number and percentage of subjects. A subject is only counted once per PT and is summarized according to their highest severity and closest relationship. A subject may have multiple PTs.

²Any SAE occurred will be summarized in the footnote.

Table 14: Severity of adverse events and their relatedness to study by MedDRA® system organ class and preferred term, and treatment dose (continued)**Treatment emergent adverse events (TEAE)**

MedDRA® System Organ Class (SOC)	MedDRA® Preferred Term (PT)	G-Pen™ Dose																			
		0.5 mg (N=X)										1.0 mg (N=X)									
		Severity				Relatedness				Severity				Relatedness				Study Drug		Study Device	
		Mild		Moderate		Severe		Study Drug		Study Device		Study Procedure		Mild		Moderate		Severe		Study Drug	
		n	%	n	%	n	%	n	%	n	%	n	%	n	%	n	%	n	%	n	%
Any SOC	Any PT	xx	xx.x	xx	xx.x	xx	xx.x	xx	xx.x	xx	xx.x	xx	xx.x	xx	xx.x	xx	xx.x	xx	xx.x	xx	xx.x
[SOC 1]	Any PT	xx	xx.x	xx	xx.x	xx	xx.x	xx	xx.x	xx	xx.x	xx	xx.x	xx	xx.x	xx	xx.x	xx	xx.x	xx	xx.x
	[PT 1]	xx	xx.x	xx	xx.x	xx	xx.x	xx	xx.x	xx	xx.x	xx	xx.x	xx	xx.x	xx	xx.x	xx	xx.x	xx	xx.x
	[PT 2]	xx	xx.x	xx	xx.x	xx	xx.x	xx	xx.x	xx	xx.x	xx	xx.x	xx	xx.x	xx	xx.x	xx	xx.x	xx	xx.x
[SOC 2]	Any PT	xx	xx.x	xx	xx.x	xx	xx.x	xx	xx.x	xx	xx.x	xx	xx.x	xx	xx.x	xx	xx.x	xx	xx.x	xx	xx.x
	[PT 1]	xx	xx.x	xx	xx.x	xx	xx.x	xx	xx.x	xx	xx.x	xx	xx.x	xx	xx.x	xx	xx.x	xx	xx.x	xx	xx.x
	[PT 2]	xx	xx.x	xx	xx.x	xx	xx.x	xx	xx.x	xx	xx.x	xx	xx.x	xx	xx.x	xx	xx.x	xx	xx.x	xx	xx.x

¹Note: This table presents number and percentage of subjects. A subject is only counted once per PT and is summarized according to their highest severity and closest relationship. A subject may have multiple PTs.

²Any SAE occurred will be summarized in the footnote.

Listing 2: Abnormality in the physical examination evaluation at screening

Subject ID	Age Group	Physical Exam	Abnormal Finding

Table 15: Vital signs before and after administration of G-Pen™ by age group and by treatment dose for subjects aged 12.0-<18.0**Age Group: 2.0-<6.0 years (N=X)**

	Time					Change from Baseline ^a	
	Baseline	30 minutes	60 minutes	120 minutes	180 minutes	Max Increase	Max Decrease
Heart Rate, beats/min							
N	x	x	x	x	x	x	x
Mean (SD)	xxx.x (xxx.x)	xxx.x (xxx.x)					
Median	xxx	xxx	xxx	xxx	xxx	xxx	xxx
[Min-Max]	[xxx-xxx]	[xxx-xxx]	[xxx-xxx]	[xxx-xxx]	[xxx-xxx]	[xxx-xxx]	[xxx-xxx]
Systolic BP, mmHg							
N	x	x	x	x	x	x	x
Mean (SD)	xxx.x (xxx.x)	xxx.x (xxx.x)					
Median	xxx	xxx	xxx	xxx	xxx	xxx	xxx
[Min-Max]	[xxx-xxx]	[xxx-xxx]	[xxx-xxx]	[xxx-xxx]	[xxx-xxx]	[xxx-xxx]	[xxx-xxx]
Diastolic BP, mmHg							
N	x	x	x	x	x	x	x
Mean (SD)	xxx.x (xxx.x)	xxx.x (xxx.x)					
Median	xxx	xxx	xxx	xxx	xxx	xxx	xxx
[Min-Max]	[xxx-xxx]	[xxx-xxx]	[xxx-xxx]	[xxx-xxx]	[xxx-xxx]	[xxx-xxx]	[xxx-xxx]

SD= standard deviation; BP= blood pressure.

^a Positive value indicates an increase from baseline and negative value indicates a decrease.

Table 14: Vital signs before and after administration of G-Pen™ by age group and by treatment dose for subjects aged 12.0-<18.0**Age Group: 6.0-<12.0 years (N=X)**

	Time					Change from Baseline ^a	
	Baseline	30 minutes	60 minutes	120 minutes	180 minutes	Max Increase	Max Decrease
Heart Rate, beats/min							
N	x	x	x	x	x	x	x
Mean (SD)	xxx.x (xxx.x)	xxx.x (xxx.x)					
Median	xxx	xxx	xxx	xxx	xxx	xxx	xxx
[Min-Max]	[xxx-xxx]	[xxx-xxx]	[xxx-xxx]	[xxx-xxx]	[xxx-xxx]	[xxx-xxx]	[xxx-xxx]
Systolic BP, mmHg							
N	x	x	x	x	x	x	x
Mean (SD)	xxx.x (xxx.x)	xxx.x (xxx.x)					
Median	xxx	xxx	xxx	xxx	xxx	xxx	xxx
[Min-Max]	[xxx-xxx]	[xxx-xxx]	[xxx-xxx]	[xxx-xxx]	[xxx-xxx]	[xxx-xxx]	[xxx-xxx]
Diastolic BP, mmHg							
N	x	x	x	x	x	x	x
Mean (SD)	xxx.x (xxx.x)	xxx.x (xxx.x)					
Median	xxx	xxx	xxx	xxx	xxx	xxx	xxx
[Min-Max]	[xxx-xxx]	[xxx-xxx]	[xxx-xxx]	[xxx-xxx]	[xxx-xxx]	[xxx-xxx]	[xxx-xxx]

SD= standard deviation; BP= blood pressure.

^a Positive value indicates an increase from baseline and negative value indicates a decrease.

**Table 14: Vital signs before and after administration of G-Pen™ by age group and by treatment dose for subjects aged 12.0-<18.0
(continued)**

Age Group: 12.0-<18.0 years with a dose of 1.0 mg (N=X)

	Time					Change from Baseline ^a	
	Baseline	30 minutes	60 minutes	120 minutes	180 minutes	Max Increase	Max Decrease
Heart Rate, beats/min							
N	x	x	x	x	x	x	x
Mean (SD)	xxx.x (xxx.x)	xxx.x (xxx.x)					
Median	xxx	xxx	xxx	xxx	xxx	xxx	xxx
[Min-Max]	[xxx-xxx]	[xxx-xxx]	[xxx-xxx]	[xxx-xxx]	[xxx-xxx]	[xxx-xxx]	[xxx-xxx]
Systolic BP, mmHg							
N	x	x	x	x	x	x	x
Mean (SD)	xxx.x (xxx.x)	xxx.x (xxx.x)					
Median	xxx	xxx	xxx	xxx	xxx	xxx	xxx
[Min-Max]	[xxx-xxx]	[xxx-xxx]	[xxx-xxx]	[xxx-xxx]	[xxx-xxx]	[xxx-xxx]	[xxx-xxx]
Diastolic BP, mmHg							
N	x	x	x	x	x	x	x
Mean (SD)	xxx.x (xxx.x)	xxx.x (xxx.x)					
Median	xxx	xxx	xxx	xxx	xxx	xxx	xxx
[Min-Max]	[xxx-xxx]	[xxx-xxx]	[xxx-xxx]	[xxx-xxx]	[xxx-xxx]	[xxx-xxx]	[xxx-xxx]

SD= standard deviation; BP= blood pressure.

^a Positive value indicates an increase from baseline and negative value indicates a decrease.

**Table 14: Vital signs before and after administration of G-Pen™ by age group and by treatment dose for subjects aged 12.0-<18.0
(continued)**

[figure not shown]
Age Group: 12.0-<18.0 years with a dose of 0.5 mg (N=X)

	Time					Change from Baseline ^a	
